At present, maintenance hemodialysis (MHD), globally, is the most common method of renal replacement treatment (RRT) for patients with end-stage renal diseases (ESRD). As a core technical problem of MHD, functional vascular access is the base of proceeding the treatment. It is well accepted as an important acknowledgment that native arterovenous fistulas (AVF) should be the first choice for vascular access. The construction of a functional AVF can be challenging, and high initial failure rates have been reported in many publications. Estimates of non-maturation rates vary from 10% to 33% in AVF. However, there are no well-established criteria that define fistula maturation. According to the vascular access guidelines of the National Kidney Foundation Kidney Disease Outcomes Quality Initiative (NKF-KDOQI), mature permanent access has a flow of approximately 600 mL/min and a minimum diameter of 0.6 cm and is less than 0.6 cm below the surface of the skin. The arterialized veins of AVF should have a flow of more than 500 mL/min and a diameter larger than 0.5 cm, and be less than 0.6 cm deep according to the Chinese Expert Consensus of Vascular Accesses for Hemodialysis. Even when the Chinese standard was considered, there were 31.2% (101/324 patients) non-mature AVF in stable long-term (more than six months) MHD patients in eight hemodialysis centers in our previous cross-sectional study. However, their AVF could support enough flow to get an effective urine clearance ratio ($Kt/V > 1.2$) during every hemodialysis session, which should be regarded as the functional accesses in our opinion. What are the differences between functional but non-mature AVF and function-and-maturation AVF? To the best of our knowledge, rarely there are reports on the functional access. Thus, in order to identify the characteristics of functional access in newly set-up AVF in MHD patients, we designed the prospective cohort study.

2. Aim of the study

To describe the ultrasound characteristics of newly set-up arteriovenous fistulas (AVF), also to identify predictors for maturation of AVF in the forearm.

To test the benefits of the ultrasound following-up protocol on AVF in MHD patients.

3. Methods

3.1 Patients

Patients beginning MHD treatment in Peking University International Hospital from July 2016 will be screened. If patients fit to the selection criteria, they might be enrolled into the present study. Enrolled patients were divided into intervention group and control group.

3.1.1 Entry criteria:

- ① Regular hemodialysis patients (4 hours per session and three times a week).
- ② Planning to construct a new radiocephalic AVF in forearm.
- ③ 18-70 years old.

3.1.2 Exclusion criteria:

- ① Predicted duration of MHD less than six months, such as transferring to peritoneal dialysis, planning to kidney transplantation, or short life expectancy, etc.
- ② Have the following complications: malignant tumors, active rheumatism, malnutrition and cachexia.
- ④ Acute renal dysfunction.
- ④ Having done any blood vessel operations on the same side of the arms that planned to create an AVF. But it was not been care in the present study whether there were vascular accesses or not in the contralateral arm.
- ⑤ Not accepted AVF personally.
- ⑥ Other kinds of vascular accesses, such as brachiocephalic AVF, upper limb AVF, graft accesses, and so on.

3.2 Detection and following up of the intervention group:

The basic information of the patients, including gender, age, dialysis length, hemodialysis access, and primary causes of renal failure, will be collected. The baseline data will be recorded, including height, weight, BMI, and blood pressure (BP). Ultrasonography detection on the forearm blood vessels would be conducted before the surgery of AVF creation (time 0, t0). The operations will be conducted by a certain nephrologist with more than ten years experience of doing AVF surgeries. Until the patients finish the AVF operation, they would be followed up at least six months.

During following up, vascular ultrasound examinations for assessment of AVF are proceed at the end of two weeks (t1), two months (t2), three months (t3), and six months after operation (t6), regularly. When patients are detected by ultrasound, they lie down and expose the arm completely. The distal segment of brachial artery (a1), proximal segment of radial artery (a2) and ulnar artery (a3), distal segment of radial artery (a4) and ulnar artery (a5), cephalic vein draining segment nearly 0.5 cm far from the anastomosis (a6), and cephalic vein downstream segment nearly 0.5cm far from a6 (a7) should be examined by linear transducer with higher-frequency (3-12 MHz) using Philips Ultrasound equipment (HD11XE, CX50, IU22, Philips Ultrasound, USA.)

(Figure 1) .The sonographic evaluation parameters including lumen diameter (D), resistance index (RI), blood flow volume (BFV) of every vascular segment above will be measured and recorded. These evaluations are performed by two experienced radiologists in ultrasound, respectively, and all results would be averaged. The procedure of ultrasound examination follows the suggestion of America Institute of Ultrasound in Medicine (AIUM).

[figure not shown]

Figure 1 Ultrasound examination sites of arteriovenous fistula in forearm

The sign of a1 is the distal segment of brachial artery, a2 is the proximal segment of radial artery, a3 is the proximal segment of ulnar artery, a4 is the distal segment of radial artery, a5 is the ulnar artery, a6 is the cephalic vein draining segment nearly 5 cm far from the anastomosis, and a7 is the cephalic vein downstream segment more than 5 cm far from a6.

Physical examination would be performed by experienced nurses to decide if the AVF could be punctured for MHD at the end of third month after operation. The urine clearance index of Kt/V is calculated once per month by simple single pool module, which using pre- and post-dialysis blood urine concentrations in one midweek hemodialysis session when the AVF punctuation begin. The first testing of Kt/V was performed after three times successful cannulations of the new AVF during hemodialysis treatments. If there were several values of Kt/V , mean value of Kt/V would be calculated and been used in statistic analysis.

All AVF give a dialysis session of mean $Kt/V > 1.2$ would be defined as a functional access. If the $Kt/V \leq 1.2$ and uncapable cannulation repeatedly, the AVF is certified as dysfunctional. The enrolled patients with functional AVF will be divided into Maturation group (Group M) and Non-maturation group (Group N). Mature AVF is defined as both $BFV(t3) > 500 \text{ ml/mL}$ and $D(t3) > 0.5 \text{ cm}$, otherwise, the AVF would be stated as non-maturation. Because the distance from skin to AVF veins in forearm is seldom larger than 0.6 cm in Chinese MHD patients, we ignored this parameter in this study.

All adverse events of dialysis accesses will be recorded in enrolled patients, including secondary AVF operation, thrombosis of AVF, stenosis, puncture failure, bleeding at puncture point after dialysis, and so on.

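### Does the definition of dysfunctional access leave out fistulas that could never be used, and does that affect any planned result?

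*Combined protocol and SAP*

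**What the plan says.** All the relevant rules are in section 3.2, which covers the intervention group.

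- **Functional:** an AVF with mean Kt/V above 1.2 "would be defined as a functional access".
- **Dysfunctional:** Kt/V of 1.2 or lower "and uncapable cannulation repeatedly, the AVF is certified as dysfunctional".
- **When Kt/V exists:** "The first testing of Kt/V was performed after three times successful cannulations of the new AVF during hemodialysis treatments". After that it "is calculated once per month by simple single pool module", and where there are several values the "mean value of Kt/V would be calculated and been used in statistic analysis".
- **Puncture decision:** nurses examine the arm "to decide if the AVF could be punctured for MHD at the end of third month after operation".
- **Use of the class:** "The enrolled patients with functional AVF will be divided into Maturation group" and a non-maturation group (Groups M and N). Maturity is judged from ultrasound flow and diameter at three months.
- **Access events:** these are recorded in enrolled patients, "including secondary AVF operation, thrombosis of AVF, stenosis, puncture failure" among others.

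Section 3.3 then plans comparisons between Groups M and N (baseline variables, mean Kt/V, repeated ultrasound measures), a logistic regression for maturation, and a comparison of outcome events between intervention and control.

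**The concern.** The dysfunctional rule asks for a low Kt/V together with repeated failure to cannulate. Kt/V needs three successful cannulations first. An AVF that clots early, is not passed for puncture, or never reaches three cannulations has no Kt/V and so cannot meet the rule. These are the clearest failures, and the background section itself says that initial failure is common.

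Two further gaps follow. A cannulable AVF with mean Kt/V of 1.2 or lower falls in neither class. An AVF that fails after some good months keeps its functional label, because no values exist after the failure to pull the mean down.

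The study was designed to characterise functional access in new AVFs. If its definition dropped the failures from the count, any stated functional rate would be too favourable. Late failures would also sit in Group M or N with only their pre-failure Kt/V.

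**Working it through.** The plan states no figure on this point, so there is none to reproduce. The check is to apply the rules to every case and then follow the result into section 3.3.

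**Step 1. Classes under the text.** Inputs: the two definitions and the Kt/V timing, all from section 3.2.

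| Mean Kt/V | Repeated cannulation failure | Literal *and* | *And* read as *or* |
|---|---|---|---|
| >1.2 | no | functional | functional |
| >1.2 | yes | functional | both classes |
| ≤1.2 | no | neither | dysfunctional |
| ≤1.2 | yes | dysfunctional | dysfunctional |
| none | no | neither | neither |
| none | yes | neither | dysfunctional |

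Under the literal reading, one of six combinations is dysfunctional and three have no class. Under *or*, one has no class (for example, clotted before any cannulation attempt) and one has two. Neither reading is complete.

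**Step 2. Where the class enters section 3.3.**

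- *Group M against Group N:* entry needs mean Kt/V above 1.2. Rows 3 to 6 are excluded whether they are called dysfunctional or left unlabelled.
- *Regression for maturation:* the outcome is defined by three-month ultrasound flow and diameter. The dysfunctional label is not part of it.
- *Intervention against control:* this compares outcome events. Thrombosis, puncture failure and secondary operation are recorded directly and do not pass through the label.
- *A functional proportion:* none is planned.

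The label therefore decides membership or outcome in none of the planned analyses.

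**Step 3. Size if a proportion were reported anyway.** Let F be the functional count, N all AVFs created and u the share with no class. Among classified AVFs the proportion is F/(N(1-u)); among all created it is F/N. The ratio is 1/(1-u).

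- u = 5%: 1/0.95 = 1.05
- u = 10%: 1/0.90 = 1.11
- u = 33%: 1/0.67 = 1.49

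All three values of u are assumptions. The 10% and 33% are the ends of the background section's range for non-maturation, which is a different state. The same section reports 101/324 = 31.2% non-mature AVFs among stable patients and says these still delivered Kt/V above 1.2. The upper factor therefore has no support as an estimate for never-usable AVFs.

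**Step 4. Late failure.** With assumed monthly values:

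- 1.4, 1.3, 1.0, then failure: 3.7/3 = 1.23, functional.
- One further value of 0.9: 4.6/4 = 1.15, not functional.
- With k earlier values of 1.4, the last value must be no higher than 1.2(k+1) - 1.4k for the mean to stop exceeding 1.2. That is 1.0, 0.8 and 0.6 for k = 1, 2 and 3.

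So a late failure can keep the functional label. It then contributes the Kt/V delivered while the access was in use, and the failure itself is counted as an access event.

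**The case for a change.** The strongest case for a change is that the text is defective under every reading. Literal *and* leaves gaps, *or* creates an overlap, and taking the second Kt/V as a single value rather than the mean creates another. Two analysts could give different functional rates from the same data, in a study whose stated interest is functional access. A reworded definition would cost little, since nearly all the data are already collected.

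The defect in wording stands. The consequence does not follow, because the disagreement would concern a rate the plan does not report. To get the inflated figure, an analyst would also have to choose classified AVFs as the denominator, which nothing in the plan suggests. An analyst faced with an AVF that never supported dialysis would count it as failed.

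The late-failure argument has some force, because those AVFs do enter the comparison of mean Kt/V. But the plan uses *functional* as an entry condition for splitting AVFs by three-month maturity, not as a six-month patency endpoint. Keeping delivered Kt/V and later failure as separate measures is a legitimate choice.

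Redefining *functional* as free of failure to six months has costs of its own. An AVF that clotted, was reopened and then worked well would be called dysfunctional unless a further rule were written for re-operation. Reasons and dates of leaving follow-up would have to be collected. A sensitivity analysis dropping AVFs that failed by six months would select on an outcome that arises after the groups are formed.

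**Conclusion.** No change follows. The dysfunctional rule is loosely worded and, taken literally, misses never-usable AVFs and cannulable AVFs with low Kt/V. The omission touches no analysis in section 3.3: the label is not used there, Groups M and N are the same with or without it, and the failures are captured as access events. Analysts can fill the gap without difficulty: mean Kt/V above 1.2 is functional, every other assessable AVF is not, and later failures are reported as events.

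How late failures are treated is a fair trade-off between describing the dialysis an access delivered and describing how long it lasted.

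The effect on planned results is nil. The effect on an unplanned functional proportion cannot be computed, because the documents give no number of AVFs, no never-usable rate and no Kt/V distribution. The conclusion assumes that section 3.3 is the full list of analyses. If a functional proportion were reported later, its denominator should be all AVFs created in the intervention group.

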3.3 Statistical analysis

Metrological data is expressed as mean \pm standard deviation (SD). The baseline variables are compared by independent t-test for measurement data and by χ^2 test for count data between Group M and Group N. The means of Kt/V are calculated for every patient and they are compared between two groups. Whether the AVF could be mature or not, predict factors are detected by Logistic Regression among these parameters on basement. The differences of the parameters between two groups are compared using General Linear Model Repeated Measures (GLM-RM) for continuous variables during following up. The results of GLM-RM can also identify the parameters' changes along with the timeline. The outcome events were compared between intervention group and control group. $P < 0.05$ is considered to indicate a significant difference. All of the analyses are performed using SPSS software (version 13.0 for Windows; SPSS Inc., Chicago, IL, USA).

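### Stenosis is among the events apparently compared for Aim 2, but scheduled scans that can find it are described only for the intervention group, so that comparison is biased against ultrasound

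*Combined protocol and SAP*

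**What the plan says.** Section 2 gives as the second aim "To test the benefits of the ultrasound following-up protocol on AVF in MHD patients". Section 3.1 states "Enrolled patients were divided into intervention group and control group" and does not describe what the control group receives or how it is observed.

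Follow-up is set out under the heading "3.2 Detection and following up of the intervention group". Within that section, "vascular ultrasound examinations for assessment of AVF are proceed at the end of two weeks (t1), two months (t2), three months (t3), and six months", counted from the operation. At each scan, "lumen diameter (D), resistance index (RI), blood flow volume (BFV) of every vascular segment above will be measured and recorded". No matching section exists for controls.

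Still in section 3.2, access events are to be recorded in enrolled patients, "including secondary AVF operation, thrombosis of AVF, stenosis, puncture failure, bleeding at puncture point after dialysis, and so on". No diagnostic criterion for stenosis is given, and no rule links a scan finding to a re-operation.

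The whole analysis for the second aim is one sentence in section 3.3: "The outcome events were compared between intervention group and control group". The outcome events are not defined there, and no primary event, composite or blinded assessment is named.

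**The concern.** For stenosis, the intervention under test is also a means of detection. Repeated measurement of diameter and flow along the access can show a narrowing that causes no clinical signs. Without a scheduled scan, the same narrowing may never come to notice. Recording events in all enrolled patients equalises the recording of what is noticed. It does not equalise what is looked for.

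If stenosis is compared between the groups, the scanned group can show more of it with no difference in the true course. A pooled count that includes stenosis carries the same bias. Randomisation, covariate adjustment or a larger sample would not remove it, because the difference in detection arises after allocation and is a consequence of allocation. At stake is a comparison meant to show benefit that could show apparent harm, or hide a real reduction in stenosis.

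**Working it through.** The plan gives no sample size, event rate or effect size for the second aim, so there is no design figure to reproduce. The check is first a reading of the text, then an illustration on assumed inputs.

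**Reading**

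1. The intervention is ultrasound follow-up (section 2, second aim).
2. The scan schedule appears only in the section headed for the intervention group (3.2). The text never states that controls go unscanned. If they had the same scans, however, the second aim would have no contrast to test.
3. The scan records lumen diameter and flow, which can reveal a narrowing (3.2).
4. Stenosis is in the only list of access events (3.2). That list is the only candidate for the events compared in 3.3, though 3.3 does not refer to it.
5. From 1 to 4, the chance of detecting a stenosis without clinical signs depends on group, and nothing in the plan offsets this.

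**Illustration for stenosis only (all detection rates assumed)**

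Let π be the true stenosis rate, the same in both groups, d1 the proportion detected under scheduled scans and d0 the proportion detected in controls.

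Recorded rate = π × d. Recorded ratio = (π × d1)/(π × d0) = d1/d0, so π cancels.

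| d1 | d0 | Recorded ratio, intervention to control |
|---|---|---|
| 0.90 | 0.90 | 1.00 |
| 0.90 | 0.70 | 1.29 |
| 0.90 | 0.50 | 1.80 |
| 0.90 | 0.30 | 3.00 |

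Example: with π = 30% and d0 = 0.50, the recorded rates are 0.30 × 0.90 = 27% and 0.30 × 0.50 = 15%.

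If ultrasound truly reduced stenosis with a risk ratio of 0.70, the recorded ratio would be 0.70 × d1/d0:
- d0 = 0.70: 0.70 × 0.90/0.70 = 0.90
- d0 = 0.50: 0.70 × 0.90/0.50 = 1.26
- d0 = 0.30: 0.70 × 0.90/0.30 = 2.10

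**Chance of a false significant excess**

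This uses a two-sided 5% test of two proportions (sidedness assumed), with n per group also assumed:

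Φ{ [ |p1 − p0| − 1.96 × √(2p̄(1 − p̄)/n) ] / √( p1(1 − p1)/n + p0(1 − p0)/n ) }, where p1 and p0 are the recorded rates and p̄ is their mean.

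With n = 100, d1 = 0.90 and d0 = 0.50:
- π = 10%: 9% vs 5%, chance about 20%
- π = 20%: 18% vs 10%, chance about 37%
- π = 31.2%: 28.1% vs 15.6%, chance about 57%

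The 31.2% is the non-maturation figure from the background (101/324), used only as the upper end of an assumed range. It is not a stenosis rate. Across 50 to 150 per group, the three values of π and d0 from 0.70 to 0.30, the chance runs from about 6% to 99%. With no detection gap it would be 5%/2 = 2.5% in this direction. A range this wide shows that the mechanism can matter. It does not estimate how much it does.

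**The case against.** The strongest reply is that several links are not written down. Section 3.3 does not say that the section 3.2 list is the outcome set, and the list is introduced as adverse events. Follow-up of controls is not described at all. Section 3.2 also classes enrolled patients with a functional AVF as mature or not by their three-month ultrasound values, and section 3.1 uses the term enrolled for both groups. On that reading controls would have at least one scan. Nor does any rule say that a scan finding is to be recorded as a stenosis event. All of this stands, and it limits confidence. It does not remove the point. The maturation text sits inside the intervention section, one scan against four would narrow the gap without closing it, and identical scans would leave the second aim nothing to test.

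A reader might go further and infer that ultrasound generates the secondary operations it is judged on, so that these too are a detection artefact. The documents do not support that. An operation is equally visible in both groups, and no passage ties it to a scan result. If scanning does prompt more operations, that is a real consequence of the protocol and belongs in the judgement of benefit.

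A reader might also infer that a real reduction in thrombosis would be hidden and that the second aim as a whole could not be interpreted. That would require a pooled count, and none is specified. Thrombosis can be compared on its own as the plan stands, and it depends much less on scanning, as do puncture failure and bleeding.

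Finally, the ratios above restate the assumed detection rates. They are not evidence of size.

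**Conclusion.** The point holds for stenosis and for any pooled count that includes it. As written, the plan would tend to record more stenosis in the scanned group even if the true course were identical, so that comparison is biased against ultrasound. It rests on two inferences: that the section 3.2 list supplies the events compared in section 3.3, and that controls have no scheduled scans. The size is unknown. The recorded ratio would be 1.3 to 3.0 if 90% of stenoses were detected with scans and 70% to 30% without, all assumed.

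Secondary AVF operation is a matter of interpretation, not of ascertainment, because scan findings may prompt it. The point should be fixed but does not undermine every comparison under the second aim. Confidence is moderate.

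**What to change.** In section 3.3:

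- Define the events for the second aim as those that do not need a scheduled scan to be found: thrombosis of the study AVF and loss of the study AVF for dialysis, within six months of operation. Define loss in advance. Six months matches the minimum follow-up in section 3.2.
- Report stenosis descriptively. Keep it out of the between-group test and out of any pooled count.
- Compare all secondary AVF operations between groups as a separate outcome. Also report them by trigger (scheduled scan or clinical signs). Scan-prompted operations stay in the comparison, so the procedure burden remains visible beside any reduction in thrombosis.

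In section 3.2, state how these events are recorded in controls, and use the same method in both groups. Say there whether controls have any scheduled scans.

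The cost is wording in two sections and one extra data field for the reason for re-operation. No visits or procedures are added. The downside is fewer countable events, and so less power, in the comparison for the second aim.
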